## **The Role of Adherent Occlusive Antimicrobial Absorbent Foam Dressing in Prevention of Cesarean Section Wound Complications**

### **Background and Significance:**

Cesarean delivery rates continue to increase in the United States, accounting for 33% of all births in 2011 (1). Patients undergoing cesarean delivery are at a greater risk of postpartum infection when compared to vaginal delivery. Additionally, the most prominent risk factor for postpartum infection is cesarean delivery. The spectrum of puerperal infections ranges from surgical site infections (SSI), endometritis, and abscess to pelvic thrombophlebitis, bacteremia, and sepsis (2). 2.5-16% wound complication post csection which includes seroma, hematoma, infection, separation and dehiscence. Risk factors for wound complication include medical disorders such as diabetes, tobacco use, preeclampsia, obesity, frequent vaginal exams, internal monitoring and emergent cesarean. (3) Reported rates of post-cesarean wound infection range from 2.71-11.4% (4-8). Risk factors for post-cesarean SSIs include prolonged operating time, body mass index (BMI) greater than 30, and increased thickness of subcutaneous tissue (5,6). Furthermore, patients undergoing cesarean delivery experience increased risk of rehospitalization within 30 days postpartum, as the majority of SSIs become apparent following discharge (9, 10). SSI is the principal reason for readmission following cesarean delivery (9).

Wound infection is an economic and social burden to the health care system. Of the major health care-associated infections—central line-associated bloodstream infection, ventilator-associated pneumonia, SSI, Clostridium difficile infection, and catheter-associated urinary tract infection—SSI contributes the most to the total annual cost of health care-associated infections (11,12).

The increased risk of postpartum infection following cesarean delivery has motivated research to establish practices now accepted as standards of care. The routine use of prophylactic antibiotics in women undergoing cesarean delivery reduces the risk of fever, wound infection, endometritis, serious infectious morbidity, maternal urinary tract infections, and decreased maternal length of stay in the hospital (13). Vaginal cleansing with an antiseptic solution immediately prior to cesarean delivery reduces the risk of endometritis but has not been found to reduce the number of fevers or wound complications (14). However, despite these measures, post-cesarean wound complications, with disruption and/or infection still occurs.

Of the heavy metals, silver possesses antibacterial activity and thus, has been used in medicine for centuries. Well-known uses of silver include silver nitrate drops to

prevent gonococcal ophthalmia neonatorum and silver sulfadiazine to prevent burn wound infections (15). While the antimicrobial mechanism of silver is not completely understood, proposed pathways include oxidative destruction catalyzed by silver, targeting of membrane proteins, affinity for sulfhydryl groups, and blocking or destroying host-cell receptors (16).

Silver-containing wound dressings and topical agents are widely used for burn injuries and chronic wounds, such as ulcers. Wound dressings and creams containing silver may help promote wound healing as well as prevent local infections. The use of silver for wound management is limited and, as a result, the literature investigating its use and recommendations for its use in wound management remain inconclusive. In a recent prospective, randomized controlled trial involving SSI following colorectal surgery, the total incidence of SSI was significantly lower in the silver nylon dressing group versus the control group (17). However, other studies have failed to show a statistically significant reduction in SSIs with the use of silver-impregnated dressings (18-20).

Evidence to support the use of silver-containing dressings to limit and treat post-cesarean SSIs is particularly limited. Connery et al. (2012) conducted a retrospective review to evaluate the effectiveness of silver-containing dressings versus traditional wound dressings in reducing additional postoperative visits associated with SSIs in patients undergoing cesarean delivery. Although they did not find a significant difference between the experimental and control groups, the study was limited due to small number of study subjects and a higher number of medical comorbidities in the study group (21).

Despite measures to decrease the risk of postpartum infection following cesarean delivery, the rate of SSI remains prominent. Wound infections are responsible for longer hospital stays, readmissions, and ultimately, increased costs to the healthcare system. Silver-containing dressings may prevent wound infection. The purpose of the current study is to determine if the use of a silver-impregnated dressing decreases the incidence of SSI following cesarean delivery.

**Purpose:** To investigate the role of an adherent soft silicone anti-microbial occlusive foam silver-impregnated dressing for primary cesarean delivery.

**Primary Aims:**

1. To determine the primary cesarean wound complication rate using the adherent soft silicone silver impregnated anti-microbial occlusive foam dressing silver-impregnated dressing

**Secondary Aims:**

1. To assess pain scores by VAS in primary C-section patients using the adherent soft silicone silver impregnated anti-microbial occlusive foam dressing silver-impregnated dressing

2. To assess cosmetic appearance of the incision based on Stony Brook scar evaluation scale scores for those patients using the adherent soft silicone silver impregnated anti-microbial occlusive foam dressing silver-impregnated dressing.

## **Methods and Materials**

### *Study Population and Recruitment*

This single-center, prospective, observational trial will include women between 18 and 45 years of age with viable pregnancies (24 weeks or greater) undergoing primary cesarean delivery at Loyola University Medical Center, Maywood, Illinois.

### ***Inclusion criteria:***

Participants must meet all of the following criteria:

- Consent to undergo cesarean delivery
- Between the ages of 18 and 45
- Primary C-section
- Subcuticular skin closure
- Able to consent, fill out study documents, and complete all study procedures and follow-up visits

### ***Exclusion criteria:***

- Patients with an allergy to silver
- Inability to obtain informed consent
- Staples
- Repeat C-section
- Vertical skin incision
- Intrapartum fever of 100F or >

## **Enrollment**

Women will be approached for voluntary study participation upon admission to labor and delivery or the antepartum unit. A member of the research team will explain the purpose and procedures of the study. Potential participants who meet the inclusion criteria and sign the research consent document will be enrolled. A signed copy of the research consent document will be given to the subject. The investigator will keep the original research consent document, in keeping with prevailing research regulations.

## **Protection of Human Subjects**

### *Recruitment and Informed Consent*

Participants will be counseled by the study personnel (investigator or study coordinator) prior to signing informed consent for study participation. All study procedures will be approved by the LUMC Institutional Review Board.

### Protection and Informed Consent

This protocol will comply with all prevailing regulations that govern human subject research. Our research team is directly responsible for monitoring the safety of study participants. All adverse events will be documented and reported to our IRB in a timely manner. Finally, the research team and our IRB will report serious adverse events that affect study conduct to the appropriate NIH program officers.

In addition, strict research procedures will be followed to minimize risks to the privacy of participants. Patient identifiers will not be included on any study documents, and identifying information will not appear in any electronic database. Once a patient consents to join the study, they will be assigned a study ID number, which will then be used to refer to that patient for the duration of the study. Documents linking patient identifiers and study ID will be kept in a locked cabinet, separate from other study documents.

### **Study Flow and Measurements**

As part of clinical care, all patients who are admitted to Loyola's labor and delivery or antepartum unit undergo a standardized history and physical examination. At the time of recruitment for the study, all study participants will undergo a standardized baseline obstetric evaluation, which includes:

- Demographics: age, self-reported race and ethnicity, medications, allergies, prior medical and surgical history, obstetric and gynecologic history
- Examination: gestational age, maternal BMI, rupture of membranes, labor, temperature, blood pressure

### **Methodology of Measurements:**

Women who are admitted to labor and delivery or the antepartum unit will be invited to participate. Those who require a cesarean delivery will undergo standard perioperative management: surgical skin preparation with Chloroprep solution, vaginal betadine prep, and prophylactic antibiotics. Women, who consented to participate, have a Pfannensteil incision and subcuticular skin closure will have the study dressing, *Mepilex Border AG*, placed.

*Mepilex Border Ag* is produced by Molynycke Health Care, and is a commercially available adherent soft silicone anti-microbial occlusive foam silver-impregnated dressing. This dressing was designed to aid in healing of wounds at high risk for infection, such as postoperative wounds, with provision of localized antimicrobial

activity. The high risk for wound infection and complications in our population led to selection of this dressing. No contraindications have been identified.

The cesarean delivery technique may differ among health care providers at our institution but generally follows usual practice, including perioperative prophylactic antibiotics and surgical skin preparation with Chloroprep solution, vaginal betadine prep, saline irrigation of the subcutaneous layer, and the use of cautery to obtain hemostasis. In addition, the subcutaneous layer is reapproximated with 3-0 Vicryl for all women with a subcutaneous layer greater than 2.0 cm. The skin will be closed with continuous absorbable suture, e.g. 3-0 Vicryl or Monocryl. Women with subcuticular suture will have adhesive strips applied with benzoin prior to the placement of the dressing.

If not participating, the wound will be dressed with a standard dressing. The standard dressing will be removed by 24 hours postoperatively. The study dressing will be removed during the first 7 days post-op only to allow/require dressing changes due to clinical signs of infection, leakage, or if the dressing falls off. Otherwise the study dressing will be removed on postoperative day 7 by a physician.

Obstetric physicians will perform a standardized physical examination of the wound dressing on each postoperative day, at 7 days post-operatively on dressing removal, and the wound will be examined also at the standard 6 weeks postpartum examination for patients in both groups. For patients who do not return for their postpartum visit at 7 days and 6 weeks, a standardized phone evaluation will be conducted by trained study personnel; any report of wound complication will be documented in the medical record.

The **primary outcome variable** will be a composite of wound disruption and/or infection occurring within 4 weeks postoperative (**wound complication rate: SSI**). Wound disruption will be defined as any separation of the wound (ranging from small skin defects to entire separation of the wound) and subcutaneous skin dehiscence, i.e. from seroma or hematoma. Wound infection will be classified by the Centers for Disease Control and Prevention (CDC) guidelines (22). **Secondary outcomes will include:** pain measured at 24h, 48 h, 7 days at dressing removal, and 6 weeks after cesarean delivery using a ten-point visual analog scale (VAS) from 0 to 10 (with 0 indicating no pain and 10 indicating worst conceivable pain), cosmesis score (as defined by the Stony Brook Scar Evaluation Scale (23)) 7 days and 6 weeks postoperatively, mobility assessment, readmission to the hospital, post discharge fever or antibiotic therapy, and additional clinic visits (both routine and unscheduled). Please see Figures 1 and 2. Additionally, all patients will be queried on degree of satisfaction on a scale of 1-10 as will clinicians queried on ease of use.

In addition, deidentified demographic and outcome data on those who had a primary csection with transverse incision closed in a subcuticular fashion who did not participate in the silver dressing during the same time period were collected.

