## Analysis Plan

### Statistical Considerations:

*Data Management:* Data forms collected will be converted to equivalent electronic data entry forms with use of REDCap. REDCap (Research Electronic Data Capture) is a secure, web-based application designed to support data capture for research studies, providing: 1) an intuitive interface for validated data entry; 2) audit trails for tracking data manipulation and export procedures; 3) automated export procedures for seamless data downloads to common statistical packages; and 4) procedures for importing data from external sources. REDCap is hosted on secure servers located in the Loyola Medical School Campus and supported by the IT department. Project staff will be trained in the use of REDCap for entry of study data. Appropriate logic and limits checking (including cross-form validity checks) will be implemented in REDCap to facilitate accurate and consistent data entry. Study information within the virtual environment will be available for participant tracking activities such as production of result and reminder letters, scheduling of interim telephone contacts, and scheduling and tracking of follow-up visits.

*Statistical Analysis:* It has been argued that the current rate of wound complication is about 10%. We postulate that patients following this treatment will experience a lower rate of wound complication. The incidence of infection will be estimated as the proportion of patients who developed infection by the end of the study period. Confounded-adjusted rates will be estimated using generalized linear models (identity link, binomial family). We will apply a one-sample, two-sided, 5% significance Z-test to compare the rate of infection with the new treatment to the historical 10%.

In addition, comparisons between the silver dressing group and the contemporary comparison group will be made by T-test, Chi-square, Fishers exact test, logistic regression modeling.

[figure not shown]
*Sample Size/Power Justification:* As stated above, we are interested in demonstrating that the rate of wound complication is lower than the historical 10% value found in the literature. We will accrue **185 patients** to detect a 5% difference (10% vs 5%) using the one-sample Z-test with 80% statistical power. Testing via the generalized linear model to adjust for confounders will increase the statistical power to detect differences.

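### The comparison of dressing women with the contemporary group is at serious risk of detection bias, because the plan gives no matching route for finding wound complications in non-participants

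*Combined protocol and SAP*

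**What the plan says.** The primary outcome is "a composite of wound disruption and/or infection occurring within 4 weeks postoperative" (Methodology of Measurements). Disruption has a low threshold: "any separation of the wound (ranging from small skin defects to entire separation of the wound" counts.

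The same section describes the follow-up. Physicians examine the dressing on each postoperative day and again at 7 days, when it is removed. They examine the wound at the routine 6-week visit, and the sentence ends by referring to both groups. The study dressing normally stays on until a physician takes it off on day 7. For women not participating, "The standard dressing will be removed by 24 hours postoperatively". For patients who do not return, "a standardized phone evaluation will be conducted by trained study personnel; any report of wound complication will be documented in the medical record"; no group is named.

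The comparison group appears only in the last paragraph of that section, as "deidentified demographic and outcome data on those who had a primary csection with transverse incision closed in a subcuticular fashion" who did not participate, over the same period. No source, assessor or visit schedule is given for their outcomes.

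Under Statistical Considerations, the main analysis is stated as "We will apply a one-sample, two-sided, 5% significance Z-test" against a historical 10%, with 185 women "to detect a 5% difference (10% vs 5%) using the one-sample Z-test with 80% statistical power". As an addition, "comparisons between the silver dressing group and the contemporary comparison group will be made by" t-test, chi-square, Fisher's exact test and logistic regression.

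**The concern.** A two-group comparison of event rates is fair only if an event has about the same chance of being recorded in either group. Here one group is followed prospectively under a study schedule, and the other is a de-identified data set on women outside the study. The outcome counts minor skin defects, which are sensitive to how often and when someone looks. The Background also says that most surgical site infections show themselves after discharge, which is where follow-up appears to diverge.

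If detection differs, the observed contrast mixes the dressing's effect with the intensity of follow-up. Logistic regression on baseline factors does not help, because an unrecorded event is not a baseline imbalance. This is the study's only concurrent comparison, so readers are likely to lean on it.

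**Working it through.** **1. The follow-up, side by side** (all from Methodology of Measurements)

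| Contact | Dressing group | Comparison group |
|---|---|---|
| Dressing off | Day 7, by a physician | By 24 hours |
| Day-7 examination | Yes, at dressing removal | No dressing left to remove; not clearly provided |
| Phone call to non-returners | Yes | Not excluded, but these are non-participants held as de-identified data |
| 6-week wound examination | Yes | Yes |
| Source of outcome data | Study examinations and calls | Not stated |

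The composite closes at 4 weeks. The day-7 visit is the only scheduled post-discharge examination inside that window. The examination clearly shared by both groups falls at 6 weeks, when a small early defect may have healed.

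**2. The plan's own sample size.** For a one-sample Z-test, n = [(z_α√(p0(1−p0)) + z_β√(p1(1−p1)))/(p0−p1)]², with p0 = 0.10 and p1 = 0.05.
- Two-sided 5%, as stated: [(1.960 × 0.300 + 0.842 × 0.218)/0.05]² = 238.0, so 239.
- One-sided 5%: [(1.645 × 0.300 + 0.842 × 0.218)/0.05]² = 183.3, so 184.

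The stated 185 therefore fits a one-sided test. That is a separate matter. What counts here is that 185 is the dressing group alone, and no size is stated for the comparison group. A two-sided 5% two-group test of 10% versus 5% with 80% power would need 435 per group.

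**3. Illustration of unequal detection.** Assumptions not in the documents: 185 women in each group, every dressing-group event recorded, and 10%, 20% or 30% of comparison-group events unrecorded. Observed comparison rate = true rate × (1 − fraction unrecorded). The test is a pooled two-proportion Z-test, two-sided 5%, with

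s0 = √(2p̄(1−p̄)/185) and s1 = √((pD(1−pD) + pC(1−pC))/185), where p̄ = (pD + pC)/2.

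Power = Φ((|d| − 1.96·s0)/s1) plus the small opposite tail, where d = pD − pC.

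Example, 5% versus 10%: s0 = 0.02739, s1 = 0.02726, Φ((0.05 − 0.0537)/0.02726) = Φ(−0.135) = 0.446. For 5% versus 7%: s0 = 0.02469, s1 = 0.02467, Φ(−1.151) = 0.125, plus 0.003 in the other tail, gives 0.128.

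| Comparison events unrecorded | True 10% vs 10%: false excess with dressing | Chance of a significant difference | True 5% vs 10%: observed rates | Observed risk ratio | Power |
|---|---|---|---|---|---|
| 0% | 0 points | 0.050 | 5% vs 10% | 0.50 | 0.446 |
| 10% | 1 point | 0.062 | 5% vs 9% | 0.56 | 0.325 |
| 20% | 2 points | 0.103 | 5% vs 8% | 0.62 | 0.215 |
| 30% | 3 points | 0.178 | 5% vs 7% | 0.71 | 0.128 |

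In the last row, 0.177 of the 0.178 is the chance of wrongly finding the dressing worse.

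**4. The same sum the other way.** With equal true rates of 10%, leaving 10-30% of dressing-group events out of the count gives 9%, 8% or 7% against 10%: a false benefit of 1-3 points. The direction depends on which group is under-counted.

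**The case against.** A reader might infer that the plan denies comparison women the day-7 examination and the phone calls, and that the comparison is therefore biased against the dressing. The documents do not go that far.

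- The sentence listing the examinations ends with a reference to both groups, which can be read as covering the whole schedule. The tie to dressing removal and the 24-hour rule make the narrower reading more natural, but it remains a reading.
- The phone-call sentence names no group. De-identification alone does not rule out calls: under Protection and Informed Consent, participants' identifiers are also kept out of the database, with a separate link file. However, that section gives study IDs only to women who consent, so calls to non-participants are unlikely.
- The direction is not certain. The study dressing normally hides the wound until day 7, while comparison wounds are visible to clinicians and patients from 24 hours. Early defects could be seen sooner or more often in the comparison group.
- Both the 10-30% loss and the 185 per group are assumptions. The figures show sensitivity; they do not measure this study's bias.
- The powered analysis is the one-sample test against 10%, which does not use the comparison group.

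All of this stands, and it limits the point to a risk of bias in the additional comparison. It does not remove that risk. Even on the most generous reading, the plan still has to explain how non-participants known only through de-identified data received study examinations.

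**Conclusion.** The additional between-group comparison is at serious risk of detection bias of unknown size. The day-7 examination is tied to an event that only dressing women have, the comparison group's ascertainment route is not stated, and the planned tests cannot repair unequal detection of a composite that includes minor defects. More recorded events with the dressing is the likelier effect, which could mask a benefit or suggest harm; earlier visibility of comparison wounds could act the other way. If the assumed losses apply, a 1-3 point artefact is large beside the 5-point difference the study hopes to see, and the comparison would start from only 45% power.

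The point should be corrected before the groups are compared. It is no objection to the one-sample test. How events were ascertained for the historical 10% is also unstated, but that is a different question.

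**What to change.** 1. In Methodology of Measurements, reconcile the reference to both groups with the de-identified data on non-participants. State for each group the data source, the visits, any phone follow-up and who assessed the wound.
2. Add an event-source field in REDCap: routine care, day-7 study examination, or study phone call.
3. Report the full-composite comparison beside a prespecified sensitivity comparison on an outcome both groups can show by the same route, within the same 4-week window: a wound complication recorded in routine care that led to antibiotics, readmission or an unscheduled visit. Do not delete an event that also meets this definition because it was first seen on day 7. Simply dropping every dressing-group event found at day 7 or by phone would also remove events that routine care would have found later, and could create the false benefit shown in step 4 of the working.
4. Report each group's share with day-7 and 6-week contact, and draw a between-group conclusion only if the two comparisons agree.

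The cost is plan wording and one data field, with no new visits. The plan does not list what the comparison data contain; if event dates, treatment or visits are missing, those data would have to be extracted again. The sensitivity comparison will have fewer events and a wider interval, and minor skin defects drop out of it. Some bias remains, because events treated early at the day-7 visit may never surface in routine care.

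### The contemporary comparison group does not carry the intrapartum-fever exclusion, and the plan does not say how fever is handled in the between-group analysis

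*Combined protocol and SAP*

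**What the plan says.** All references are to the combined protocol and SAP.

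- **Exclusion criteria.** Women are excluded for "Intrapartum fever of 100F or >".
- **Enrollment.** "Women will be approached for voluntary study participation upon admission to labor and delivery or the antepartum unit", which can be well before delivery and before any fever appears.
- **Methodology of Measurements, dressing placement.** "Women, who consented to participate, have a Pfannensteil incision and subcuticular skin closure will have the study dressing". Consent, incision and closure are repeated here; fever is not.
- **Methodology of Measurements, last paragraph.** The comparators are women with a "primary csection with transverse incision closed in a subcuticular fashion who did not participate in the silver dressing during the same time period". What is collected on them is described as "deidentified demographic and outcome data on those who had a primary csection".
- **Study Flow and Measurements.** For participants, the examination at recruitment covers "gestational age, maternal BMI, rupture of membranes, labor, temperature, blood pressure". No maximum intrapartum temperature is named for either group.
- **Statistical Considerations.** "comparisons between the silver dressing group and the contemporary comparison group will be made by T-test, Chi-square, Fishers exact test, logistic regression modeling". No covariates, restriction or matching are given. Confounder-adjusted rates are promised, but the confounders are not listed.

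**The concern.** The comparator definition repeats the criteria on primary section, skin incision and skin closure, but omits the fever criterion. Non-participation does not separate eligible women who declined from women who were ineligible, so following the definition exactly admits febrile women to one group while eligibility keeps them out of the other.

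A second gap adds to this. The plan does not say whether a woman who consents on admission and then becomes febrile stays in the dressing group, becomes a comparator or is left out. If she becomes a comparator, febrile women move from one group to the other.

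If fever raises wound-complication risk, this imbalance taken alone makes the dressing look better than it is. The age limits (18 to 45) and the 24-week limit are not carried over either. That is a lesser point, since age is probably among the demographic data.

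**Working it through.** **Does anything else in the plan close the gap?**

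| Criterion for the dressing group | In the comparator definition? |
|---|---|
| Primary section | Yes |
| Transverse incision | Yes |
| Subcuticular closure | Yes |
| No intrapartum fever of 100F or more | No |
| Age 18 to 45 | No |
| 24 weeks or greater | No |

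The t-test, chi-square and Fisher's exact tests are unadjusted. Logistic regression could adjust for fever, but the plan neither names fever as a covariate nor shows that it is recorded for comparators. Participants' temperature is taken at recruitment and may precede a fever. Nothing closes the gap.

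**How large could the effect be?** The plan has no figure of its own to reproduce: 185 is the sample size for the one-sample test, and no size is given for the comparison group.

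Assumed inputs: 185 per group; a 10% rate in afebrile women of both groups (the plan's historical rate); no dressing effect; 5% to 20% of comparators febrile; relative risk with fever (RR) 1.5 to 3.

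With *fd* and *fc* the febrile shares in the dressing and comparison groups:

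- dressing rate *pd* = 0.10 × (1 + *fd* × (RR − 1))
- comparator rate *pc* = 0.10 × (1 + *fc* × (RR − 1))
- crude odds ratio (OR) = [*pd*/(1 − *pd*)] / [*pc*/(1 − *pc*)]

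Example: *fd* = 0, *fc* = 0.10, RR = 2 gives *pc* = 0.10 × 1.10 = 0.11 and OR = (0.10/0.90)/(0.11/0.89) = 0.90.

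The chance of a false result favouring the dressing is the probability that z < −1.96 in the pooled two-proportion test (the uncorrected chi-square), found by enumerating the two binomial distributions. With no imbalance it is 2.5%.

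| *fc*, RR | No fever in dressing group: OR, chance | Fever half as common in dressing group: OR, chance |
|---|---|---|
| 5%, 1.5 | 0.97, 3.0% | 0.99, 2.7% |
| 10%, 2 | 0.90, 5.0% | 0.95, 3.6% |
| 10%, 3 | 0.82, 9.0% | 0.91, 4.9% |
| 20%, 3 | 0.68, 22% | 0.84, 8.4% |

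- **Equal fever in both groups, or RR = 1:** OR 1.00, chance 2.5% to 2.6%.
- **Larger comparison group:** with 740 comparators, the worst case in the first column rises from 22% to 29%. More comparators do not remove the bias.
- **Lower base rate:** with 5% in afebrile women (the plan's target rate), the first column's chances become 2.8%, 3.9%, 6.0% and 12.1%.
- **Febrile consenters counted as comparators:** with consent share *q* and overall fever share *f*, *fc* = *f*/((1 − *q*) + *q* × *f*). For *q* = 0.5 and *f* = 0.10, *fc* = 0.10/0.55 = 18%. At RR 2, *pc* = 0.118, OR = 0.83 and the chance is 8.1%. Those shares imply 185 × 0.55/0.45 = 226 comparators for 185 dressing women, which gives 8.2%.
- **Both groups restricted to afebrile women:** OR 1.00, chance 2.5% to 2.6%.

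**The case against.** The strongest reply is about weight. The powered analysis is the one-sample test against 10%, which does not use this group. The stated aims concern only women wearing the dressing, and the comparison is an addition with no stated size, power or hypothesis. That is correct, and it limits the point to a recommended change.

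Second, the documents give no evidence that fever raises wound risk. The background says "Risk factors for wound complication include medical disorders such as diabetes, tobacco use, preeclampsia, obesity, frequent vaginal exams, internal monitoring and emergent cesarean", and its separate list for surgical site infection omits fever too. The listed factors are also uncontrolled in a self-selected comparison, so fixing fever alone does not make the groups comparable, and other imbalances could offset it. This stands: the net direction of bias is unknown. It does not excuse unequal eligibility on a factor the protocol chose to exclude.

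Third, the 22% needs high fever prevalence, a strong fever effect, a 10% base rate and no febrile women in the dressing group all at once. That is also correct, and the 5% base rate above roughly halves it.

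Fourth, the two strands pull apart: the bias needs the fever exclusion to be enforced in the dressing group, while the placement sentence leaves room for it not to be. That sentence is weak evidence that the exclusion lapses after consent, since it does not restate other criteria such as age or silver allergy either. The half-as-common and equal-fever cases cover this doubt.

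Finally, adjusting for fever with a restricted sensitivity analysis would be a legitimate alternative to restriction. It needs the same temperature field and the same prespecification.

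**Conclusion.** The concern holds. As written, the comparison group admits women whom the fever criterion keeps out of the dressing group, and the between-group analysis says nothing about fever. Adjustment is unspecified rather than ruled out.

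The size is unknown. Under the assumed inputs the effect is trivial at the low end and material only if fever is both common among comparators and a strong risk factor. The direction, toward the dressing, holds for this imbalance alone and only if fever raises wound risk. The one-sample test and the 185 are unaffected. This is a change that should be made; confidence is medium because every numerical input on fever is assumed.

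**What to change.** 1. State that comparators must meet the same eligibility limits as participants: age 18 to 45, 24 weeks or greater, and no intrapartum temperature of 100F or more.
2. Obtain maximum intrapartum temperature for both groups from the clinical record, and restrict all between-group analyses to women without intrapartum fever.
3. State that consented women who become febrile before delivery are left out of both groups in this comparison. This is an analysis rule only and does not bear on who receives the dressing.
4. If temperature cannot be retrieved, report the comparison as potentially confounded by fever.

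**Cost.** About two sentences and one main record field, plus gestational age if it was not extracted. The comparison data are described as deidentified and already collected, so a new extraction may be needed and may not be possible; step 4 covers that case.

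The loss of precision is small. The standard error of the log odds ratio is √[1/(*n₁p₁*(1 − *p₁*)) + 1/(*n₂p₂*(1 − *p₂*))]. Starting from 185 per group, with a 10% afebrile rate:

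| Febrile: dressing, comparators; RR | Before restriction | After restriction |
|---|---|---|
| 0%, 10%; 2 | 0.340 | 0.356 |
| 5%, 10%; 2 | 0.336 | 0.360 |
| 0%, 20%; 3 | 0.324 | 0.368 |
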